### **10.6.4 Combined Solicited and Unsolicited Adverse Events**

Solicited AE continuing beyond 7 days after an injection will be coded by MedDRA and combined with the unsolicited AE. An overall summary of subjects with all combined solicited and unsolicited AE, by SOC and preferred term, will be provided as well.

[REDACTED] [REDACTED] [REDACTED]

### **10.6.5 Analysis of Other Safety Data**

The frequencies and percentages of concomitant medications will be tabulated by age group, treatment group, and overall. Medications will be coded using the WHO Drug dictionary.

## **10.7 Immunogenicity Analysis**

### **10.7.1 Geometric Mean Titer, Geometric Mean Concentration, and Geometric Mean Titer Fold Rise**

Immunogenicity analyses will be performed by age group (50 to 59, 60 years and older, 65 years and older) and overall (50 years and older). Analyses will be performed for both OPA titers ( $\log_{10}$ ) and IgG titers (mcg/mL). All immunogenicity analyses will be based on the IEP and Exposed Population.

The Geometric Mean Titer (GMT) and Geometric Mean Concentration (GMC) will be analyzed via linear models. The primary model is an analysis of variance (ANOVA), with logarithmically-transformed titers ( $\log_{10}$ ) as the dependent variable and treatment group and study site as the fixed effects in the model. The results included in the main tables of the report will be based on this basic ANOVA model. As a secondary analysis, in order to remove the effect of baseline concentration on the GMT, an analysis of covariance (ANCOVA) will also be performed. The ANCOVA includes treatment group and study site as the fixed effects and  $\log_{10}$  baseline titer as the covariate in the model. The rationale for including baseline values as a covariate is that prior data have shown vaccine response is correlated with baseline antibody levels.

The least squares means and their 95% confidence intervals (CI) calculated based on the ANOVA and ANCOVA will be back transformed and reported as the group GMT and GMC values (adjusted for the mean baseline in the case of the ANCOVA). GMR will also be calculated from the ANCOVA and ANOVA models.

Comparisons between relevant groups will be based on the estimated adjusted GMT measured at Month 1 for 31 serotypes in VAX-31 (of those 20 in PCV20), and mean square error calculated from the basic ANOVA model using contrast statements. The analysis of GMFR relative to Day 1 will also be computed using similar models.

The main comparison of interest will be the 3 VAX-31 dose level groups vs the PCV20 (20 serotypes) group. However, the 3 VAX-31 dose level groups will also be compared in a pairwise fashion on a serotype-by-serotype basis. No adjustment for multiplicity will be applied, and missing data will not be imputed.

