## **10. Statistical Analysis**

This Phase 1/2 study is designed to achieve both safety and immunogenicity objectives.

The primary objectives are to evaluate the safety of a single injection of VAX-31 at 3 dose levels and to compare the safety of VAX-31 to that of PCV20 administered to 4 groups:

- Subjects aged 50 to 59 years receiving PCV20
- Subjects aged 50 years and older receiving PCV20
- Subjects aged 60 years and older receiving PCV20
- Subjects aged 65 years and older receiving PCV20

The secondary immunogenicity objectives are to assess the induction of OPA and MSD antibody responses by VAX-31 at 3 dose levels compared to the 20 PCV20 serotypes (1, 3, 4, 5, 6A, 6B, 7F, 8, 9V, 10A, 11A, 12F, 14, 15B, 18C, 19A, 19F, 22F, 23F and 33F), as measured at 30 days after the injection (Month 1) and 11 non-PCV20 serotypes (2, 7C, 9N, 15A, 16F, 17F, 20B, 23A, 23B, 31 and 35B), as compared to the standard regulatory criteria for efficacy (e.g., lower bound of the 2-sided 95% CI for the geometric mean ratio GMR for a given serotype greater than 0.5 for noninferiority of shared serotypes and the lower bound of the 2-sided 95% CI for the geometric mean ratio GMR for a given serotype greater than 2.0 for superiority of the novel serotypes), measured at 30 days after the injection (Month 1) for subjects aged 50 to 59 years, 50 years and older, 60 years and older, and 65 years and older.

A statistical analysis plan (SAP) will be generated and approved prior to the interim analysis and treatment group unblinding for the primary safety and secondary immunogenicity endpoints through Month 1 visits. Individual treatment unblinding will occur after the data are cleaned

through the last Month 6 visits and final database lock. A single completed Clinical Study Report (CSR) will summarize safety and immunogenicity findings through Month 6 for all 1000 subjects.

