### **10.7.2 Threshold Analyses**

For the 11 non-PCV20 serotypes that are in VAX-31, the % of subjects with a  $\geq 4$ -fold increase in OPA titer will be evaluated using a logistic regression model, with an indicator variable for achieving a  $\geq 4$ -fold increase in OPA titer as the dependent variable, and treatment group and study site as fixed effects and  $\log_{10}$  baseline titer as a covariate. The difference in proportions achieving a  $\geq 4$ -fold increase in OPA titer in each of the 3 VAX-31 dose levels group vs the PCV20 and the corresponding 95% CI will be calculated. If the lower bound of the 95% CI is  $>0.1$ , the VAX-31 dose will be deemed statistically superior to PCV20.

The percentage of subjects achieving specified thresholds (e.g., GMFR  $\geq 4$  in serotype-specific OPA and IgG, achieving OPA titer of at least serotype-specific LLOQ of the assay), and associated Wilson (score) 95% CI, will be calculated for the Month 1 visit data for each treatment group. A reverse cumulative distribution curve will be provided. Differences between pair-wise treatment groups may be determined via Fisher's exact tests.

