 - **GMR:** The geometric mean ratio = antilog10 (LSMeans [$\log_{10} x$]) / antilog10 (LSMeans [$\log_{10} y$]), where x and y are the 2 assays results and LSMeans is the least square means calculated by the model.
 - **Fold Ratio:** The ratio between titer/concentration at Month 1 visit and the one at Day 1.
 - **GMFR:** The geometric mean fold ratio = antilog10 (LSMeans [$\log_{10} y$]), where y is the assay fold ratio and LSMeans is the least square means calculated by the model.
 - **4-fold increase:** A subject achieved 4-fold increase if fold ratio ≥ 4
 - **BLQ:** Below lower limit of quantification (LLOQ). Per Center for Biologics Evaluation and Research (CBER) criterion, BLQ titer/concentration will be analyzed as:
 - 0.5*LLOQ for calculations of GMT/GMC and GMT/GMC Ratios (GMRs)
 - 1*LLOQ for calculations of fold ratio.
 - **ULOQ:** Upper limit of quantification. Titer/Concentration above ULOQ will be analyzed as:
 - 1*ULOQ for all calculations (GMT/GMC, GMRs, fold-ratio)

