6.2.3. Adjustments for Covariates

The randomization for Stage 1 will not be stratified.

The randomization for Stage 2 will be stratified by site.

[figure not shown]
Immunogenicity analyses:

- For the Analysis of variance (ANOVA), study site will be included as fixed effect in the model.
- For the Analysis of covariance (ANCOVA) and the logistic regression, study site will be included as fixed effect and the log baseline titer will be included as covariate in the model.

The rationale for including baseline values as a covariate is that prior data have shown vaccine response is correlated with baseline antibody levels.

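### The headline GMT, GMC and GMR results leave out baseline titre, which the plan itself calls correlated with response; the cost is precision, not validity

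*Protocol*

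**What the plan says.** Protocol 10.7.1 defines the primary model as an ANOVA on log10 titre with treatment group and study site as fixed effects, and adds: "The results included in the main tables of the report will be based on this basic ANOVA model". An ANCOVA with log10 baseline titre as a further covariate is a secondary analysis. The reason given for it is this: "The rationale for including baseline values as a covariate is that prior data have shown vaccine response is correlated with baseline antibody levels". Both models yield ratios: "GMR will also be calculated from the ANCOVA and ANOVA models". The sentence on group comparisons, however, takes the "mean square error calculated from the basic ANOVA model using contrast statements".

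SAP 6.6.1 lists the ANOVA first and the ANCOVA second and gives both the same outputs, each with its own error term. It does not repeat the primary/secondary ranking, but it draws both bar plots from the ANOVA. SAP section 7 declares no change from the protocol, so the protocol's ranking stands.

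The logistic model for a 4-fold OPA rise (protocol 10.7.2) does include log10 "baseline titer as a covariate". SAP 6.2.3 says of the ANCOVA and the logistic model together that "study site will be included as fixed effect and the log baseline titer will be included as covariate in the model".

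Protocol section 10 names the yardsticks for the ratios, as examples of regulatory criteria: "lower bound of the 2-sided 95% CI for the geometric mean ratio GMR for a given serotype greater than 0.5 for noninferiority" of the shared serotypes, and a lower bound above 2.0 for the additional ones. It does not say which model they are read from.

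**The concern.** The plan collects baseline titre on everyone, calls it correlated with the outcome, and has a model that uses it, yet leads with the model that ignores it. Neither document says why. Under randomization, adjusting for a prognostic baseline leaves the target of estimation unchanged and removes the part of the residual variance that baseline explains. Leaving it out makes the headline intervals wider than they need to be.

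The intervals concerned are the main description of each VAX-31 dose against PCV20 in a dose-finding study, in age groups whose size has no statistical justification (protocol 10.1). There is also a practical point. In any one trial, chance baseline imbalance makes the two models give somewhat different GMRs. With 31 serotypes, three doses and four age groups, the models may well fall on different sides of a bound for some comparison. The model that leads is best settled before unblinding.

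**Working it through.** **The plan's own figure.** The documents give no precision or power figure for immunogenicity. The only sample-size figures are the Stage 1 detection probabilities with 16 subjects. They reproduce (1 − 0.85^16 = 0.926 and 1 − 0.90^16 = 0.815, against 92% and 81%) but have no bearing here.

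**Inputs from the documents.** Allocation is 1:1:1:1. Subjects per arm: 65+ 200/4 = 50 and 60+ 400/4 = 100 (both from enrolment minimums), 50–59 600/4 = 150 (from a maximum), 50+ 1000/4 = 250. Intervals are two-sided 95%. The bounds are 0.5 and 2.0.

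**Assumed inputs.** SD of log10 titre (0.5 to 0.9), rho (0.1 to 0.7), and the share of baselines below the LLOQ.

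**Formulas.**
- SE of log10 GMR: SD × √(2/n) for the ANOVA, multiplied by √(1 − rho²) for the ANCOVA.
- Lower limit at an observed GMR of 1: 10^(−1.96 × SE).
- Chance of clearing a bound: Φ(log10(true GMR/bound)/SE − 1.96).

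**Interval width.** √(1 − rho²) = 0.995, 0.954, 0.866 and 0.714 at rho 0.1, 0.3, 0.5 and 0.7. The narrowing is therefore 0.5%, 5%, 13% and 29%, the same in every age group. At rho 0.5 the ANOVA would need 1/0.75 = 1.33 times the subjects to match, about 67 per arm instead of 50.

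**Worked case: 65+, SD 0.7, rho 0.5.** ANOVA SE = 0.7 × √(2/50) = 0.140; ANCOVA SE = 0.140 × 0.866 = 0.121. Lower limits are 10^(−0.274) = 0.53 and 10^(−0.238) = 0.58. Chances of clearing 0.5 at a true GMR of 1 are Φ(0.301/0.140 − 1.96) = 57.5% and Φ(0.301/0.121 − 1.96) = 69.9%.

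All groups at SD 0.7, rho 0.5 (ANOVA → ANCOVA):

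| Age group | n/arm | Lower limit at observed GMR 1 | Clears 0.5, true GMR 1 | Clears 2.0, true GMR 3 |
|---|---|---|---|---|
| 65+ | 50 | 0.53 → 0.58 | 57.5 → 69.9% | 24 → 31% |
| 60+ | 100 | 0.64 → 0.68 | 86 → 94% | 43 → 54% |
| 50–59 | 150 | 0.69 → 0.73 | 96 → 99% | 59 → 71% |
| 50+ | 250 | 0.75 → 0.78 | 99.8 → 100% | 80 → 90% |

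**Sensitivity for the 0.5 bound.**
- SD 0.5, rho 0.5: 65+ 85 → 94%, 60+ 98.9 → 99.8%.
- SD 0.9, rho 0.5: 65+ 39 → 49%, 60+ 66 → 78%, 50–59 83 → 92%, 50+ 96 → 99%. Which age group gains most in percentage points thus depends on the SD.
- SD 0.7, rho 0.3: 65+ 57.5 → 62%, 60+ 86 → 89%.
- SD 0.7, rho 0.1: about half a point or less everywhere.

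**Assay floor.** Subjects are pneumococcal-vaccine-naive (protocol 4.4.2), and SAP 5.2 sets values below the LLOQ to half the LLOQ, which weakens the observed correlation. In 2,000,000 draws with 50, 70 or 85% of baselines below the LLOQ, an underlying rho of 0.5 becomes 0.45, 0.40 or 0.33. The 13% narrowing falls to 11, 8 or 6%, and the 69.9% in 65+ falls to about 67, 65 or 62%.

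**Validity.** In 3,000 simulated trials per scenario (25 sites, SD 0.6, rho 0.3 and 0.6, 50 or 250 per arm), ANOVA coverage was 0.949–0.952 with bias of at most 0.0034 log10, and ANCOVA coverage was 0.945–0.955. Mean log10 interval widths at 250 per arm were 0.210 against 0.201 (rho 0.3) and 0.211 against 0.168 (rho 0.6).

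**Site balance.** A further simulation (SD 0.7, rho 0.5, true GMR 1, arms balanced within site) gave 57.5 → 67.9% at 50 per arm and 85.7 → 93.7% at 100 per arm. Stage 2 randomization is stratified by site and not by age, so arms need not balance within site inside an age group. Without that balance the figures at 50 per arm were 50.7 → 61.8%, with the same SE ratio of 0.868.

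**Additional serotypes.** PCV20 lacks these 11, so its arm may have a steeper baseline slope. With rho 0.3 in VAX-31 and 0.9 in PCV20, a common-slope ANCOVA, a true GMR of 3 and the 2.0 bound, the chance moved only from 24 to 26% at 50 per arm and from 44 to 52% at 100 per arm. Coverage stayed at 96–97%.

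**Disagreement between models.** The SD of the difference between the two log10 GMRs is about rho × SD × √(2/n) = 0.5 × 0.7 × 0.2 = 0.07 in 65+, a factor of 1.17.

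**The case against.** The strongest reply is that this is a preference between two valid, prespecified analyses. Both sets of GMTs, GMCs and GMRs are to be reported for both immunogenicity populations and all four age groups, so the reader loses nothing, and the SAP itself does not rank the models. That stands, and it is why this is a point about efficiency and not an error.

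It is also true that the clearing probabilities attach to no visible decision. Immunogenicity is a secondary objective, SAP 3.3 lists GMR as exploratory, SAP 6.2.4 says there are no formal hypothesis tests, and no visible section makes a dose choice depend on the bounds. The sizes rest on an assumed SD and rho, a negligible gain cannot be excluded, and for the 50+ group the effect on the 0.5 bound is trivial in the base case. The gain for the additional serotypes may be smaller than the equal-correlation table suggests.

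The comparison with the 4-fold model is only suggestive, since baseline is part of that outcome by construction. Two details of the ANCOVA are also unsettled: the analysis-set wording is per subject and not per serotype and assay, and SAP 5.2 does not name the value to use for a baseline covariate below the LLOQ.

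None of this gives a reason to prefer the less precise model as the headline. If rho is small, the change gains little and costs no validity.

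**Conclusion.** The concern holds, as an efficiency point of moderate weight. The main tables rest on a model without a covariate that the plan calls correlated with response. The ANOVA is unbiased with nominal coverage, so no result would be wrong; the headline intervals would be wider than necessary.

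The narrowing available is between 0.5% and 29% over the assumed range of rho, and 13% at rho 0.5 before any assay-floor effect. The lower limit moves most in 65+. For the 0.5 bound in 50+ the gain is nearly nil at SD 0.7 and about 3 points at SD 0.9. Confidence in the direction is high. Confidence in the size is limited, because the documents give no SD, correlation or share of baselines below the LLOQ. The figures also use planned enrolment, not the numbers left after exclusions from the Immunogenicity Evaluable Population.

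**What to change.** Before the Month 1 unblinding, make the ANCOVA (treatment, site, log10 baseline) the primary model for GMT, GMC and GMR in protocol 10.7.1 and SAP 6.6.1. Use it for the main tables, the bar plots and any reading of the 0.5 and 2.0 bounds, and keep the ANOVA as supportive. State that the ANCOVA in the Exposed Population uses subjects with a baseline result, and name the substitution rule for baseline covariates below the LLOQ. Record the change in SAP section 7.

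As a minor clean-up, align the protocol's comparison sentence with SAP 6.6.1 so that each estimate uses its own model's error term. If the adjusted means there are baseline-adjusted, pairing them with the ANOVA error gives intervals that are too wide (simulated coverage about 0.96 at rho 0.3 and 0.98 at rho 0.6).

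The cost is small but not zero: a protocol and SAP wording amendment, of which the IRB is generally informed first (protocol 11.8), reordered outputs, a headline model that differs from the current protocol, and complete-case handling in the Exposed Population. No new data or model is needed. The Immunogenicity Evaluable Population already requires a baseline result, so there the two models should use essentially the same subjects, apart from any result missing for a single serotype.

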### **10.7.2 Threshold Analyses**

For the 11 non-PCV20 serotypes that are in VAX-31, the % of subjects with a  $\geq 4$ -fold increase in OPA titer will be evaluated using a logistic regression model, with an indicator variable for achieving a  $\geq 4$ -fold increase in OPA titer as the dependent variable, and treatment group and study site as fixed effects and  $\log_{10}$  baseline titer as a covariate. The difference in proportions achieving a  $\geq 4$ -fold increase in OPA titer in each of the 3 VAX-31 dose levels group vs the PCV20 and the corresponding 95% CI will be calculated. If the lower bound of the 95% CI is  $>0.1$ , the VAX-31 dose will be deemed statistically superior to PCV20.

The percentage of subjects achieving specified thresholds (e.g., GMFR  $\geq 4$  in serotype-specific OPA and IgG, achieving OPA titer of at least serotype-specific LLOQ of the assay), and associated Wilson (score) 95% CI, will be calculated for the Month 1 visit data for each treatment group. A reverse cumulative distribution curve will be provided. Differences between pair-wise treatment groups may be determined via Fisher's exact tests.

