6.2. General Statistical Methods

6.2.1. General Methods

All outputs will be incorporated into Microsoft Word files, sorted, and labeled according to the International Conference on Harmonization (ICH) recommendations, and formatted to the appropriate page size(s).

Tabulations will be produced for appropriate demographic, baseline, safety, and immunogenicity parameters. For categorical variables, summary tabulations of the number and percentage within each category (with the number of subjects with missing data) of the parameter will be presented. For continuous variables, the mean, median, standard deviation, minimum and maximum values will be presented.

Statistical hypothesis testing will be performed on immunogenicity parameters with all tests conducted at the 2-sided, 0.05 level of significance. Summary statistics will be presented, as well as 95% confidence intervals (CI) on selected parameters, as described in the sections below.

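### For response percentages on the 20 shared serotypes, and for the IgG and LLOQ thresholds on the 11 novel ones, the only stated between-arm method is an optional Fisher's exact test; a difference with a 95% CI would report more at almost no cost.

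*Protocol*

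**What the plan says.** Protocol 10.7.2 has two parts.

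The first opens "For the 11 non-PCV20 serotypes that are in VAX-31, the % of subjects with a" 4-fold or greater rise in OPA titer. It sets up a logistic regression and a difference in proportions for each dose "vs the PCV20 and the corresponding 95% CI will be calculated". If the lower bound exceeds 0.1, "the VAX-31 dose will be deemed statistically superior to PCV20".

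The second covers threshold percentages in general: 4-fold rise in OPA and in IgG, and OPA at or above the LLOQ. It gives the percentages "and associated Wilson (score) 95% CI, will be calculated for the Month 1 visit data for each treatment group", plus a reverse cumulative distribution curve. Its only between-arm statement is "Differences between pair-wise treatment groups may be determined via Fisher's exact tests".

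Elsewhere:
- Protocol section 10 states the shared-serotype criterion on the geometric mean ratio: a lower 95% bound "greater than 0.5 for noninferiority of shared serotypes".
- SAP 3.3 lists the fold-rise and LLOQ percentages as exploratory.
- SAP 6.2.1 says "Statistical hypothesis testing will be performed on immunogenicity parameters with all tests conducted at the 2-sided, 0.05 level of significance", while SAP 6.2.4 says the study has no formal hypothesis tests.
- SAP 6.2.3 mentions a logistic regression without naming serotypes. The visible SAP does not mention Fisher's test.
- SAP section 7 declares no change from the protocol's analyses.

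**The concern.** The plan reports the same kind of endpoint in two ways. For a 4-fold OPA rise in a novel serotype, the reader gets a difference from PCV20 with an interval. For a shared serotype, or for IgG or LLOQ in any serotype, the reader gets separate arm percentages and perhaps a p-value.

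Fisher's test addresses equality only. A large p-value does not say how large a deficit remains compatible with the data. The test also runs well below its nominal level when arms are small and response rates high, which is plausible in the 65+ group. In a dose-finding study, what is at stake is how clearly the tables show the seroresponse difference between each dose and PCV20, and between doses, in older adults.

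**Working it through.** **Inputs from the documents.** Allocation is 1:1:1:1 (Protocol 6.8). There are 250 per arm overall (10.3). The 65+ group has at least 200 subjects (4.2), so about 200/4 = 50 per arm at the minimum; randomization is not stratified by age. Alpha is 0.05, two-sided (SAP 6.2.1).

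**Assumed.** The documents give no response rates. The range used is 60% to 95%.

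**The plan's own figures.** None is given for response percentages. The only computed sample-size figures are the Stage 1 detection probabilities, and they reproduce: 1 − 0.85^16 = 92.6% and 1 − 0.90^16 = 81.5%, against the stated 92% and 81%. Nothing below depends on them.

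**Step 1: true size.** For arms of n with common rate p, sum the binomial probabilities b(x1; n, p) × b(x2; n, p) over every table (x1, x2) that the method rejects. Fisher rejects at two-sided p ≤ 0.05. The score method (Miettinen-Nurminen at difference 0) rejects when |z| ≥ 1.96, with z = (x1/n − x2/n) / √[p̄(1 − p̄)(2/n) × N/(N − 1)], p̄ the pooled rate and N = 2n.

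| Common rate | Fisher, n = 50 | Score, n = 50 | Fisher, n = 250 | Score, n = 250 |
|---|---|---|---|---|
| 60% | 3.2% | 5.2% | 4.0% | 5.0% |
| 70% | 3.1% | 5.0% | 4.0% | 5.0% |
| 80% | 2.8% | 4.9% | 3.9% | 5.0% |
| 90% | 1.8% | 4.8% | 3.6% | 4.9% |
| 95% | 0.7% | 4.3% | 3.2% | 4.9% |

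**Step 2: power at 50 per arm**, by the same sum with unequal rates.

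| PCV20 vs VAX-31 | Fisher | Score |
|---|---|---|
| 80% vs 70% | 15.5% | 21.1% |
| 90% vs 75% | 41.0% | 50.8% |
| 95% vs 85% | 24.4% | 38.5% |

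Fisher costs 6 to 14 percentage points of power, but the score method is also weak. Most of the shortfall is the arm size.

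**Step 3: what the reader would see.** Take 35/50 on VAX-31 and 40/50 on PCV20.
- Fisher: p = 0.36.
- Miettinen-Nurminen 95% CI for the difference of −10 points: −26.8 to +7.2.
- The planned Wilson limits are 56.2% to 80.9% and 67.0% to 88.8%. A reader can combine them by Newcombe's method. Lower limit: −0.10 − √[(0.700 − 0.562)² + (0.888 − 0.800)²] = −0.263. Upper limit: −0.10 + √[(0.809 − 0.700)² + (0.800 − 0.670)²] = +0.070.

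The p-value alone does not show that a deficit of about 27 points is still compatible with these data. An interval does, and a close version of it can be rebuilt by hand from planned output.

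**Step 4: what the change cannot do.** With 40/50 in both arms the Newcombe interval is −15.7 to +15.7 points; with 200/250 in both it is −7.0 to +7.0. If a margin of 10 points were assumed (the documents set none), equal true rates of 80% would give a lower bound above −10 points 23% of the time at 50 per arm and 80% at 250 per arm. Results at 65+ stay descriptive under either method.

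**The case against.** The case for leaving the text alone is substantial, and most of it stands.

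- **Noninferiority is not at issue here.** A reader might infer that the plan cannot show VAX-31 responding as well as PCV20 on the shared serotypes. The documents do not support that. The criterion is the GMR lower bound above 0.5, estimated by ANOVA and ANCOVA contrasts (Protocol 10.7.1, SAP 6.6.1). No margin is set for percentages, and these endpoints are exploratory.
- **Effect information is not absent.** Per-arm percentages with Wilson limits are a firm commitment, and Step 3 shows that an approximate interval for the difference follows from them. What is missing is its presentation.
- **Fisher is not the main cause of low power at 65+.** By Step 2 the score method still misses 80% vs 70% about 79% of the time, against 84.5% for Fisher.
- **Misuse is not planned.** The test is optional. Nothing says that a non-significant result will be called similarity, and no rule ties these percentages to dose choice.
- **The public SAP may be incomplete.** It cites sections 5.5 and 6.2.5, which are not in the visible text, and nothing follows 6.6.1 although threshold endpoints are listed. A withheld section could add a between-arm interval, so the point rests on Protocol 10.7.2 and the SAP's statement of no change.
- **A second interval could compete with the first.** An unadjusted interval for the 4-fold OPA rise in the novel serotypes would sit beside the model-based one that carries the 0.1 rule. The fix must exclude that endpoint.

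What remains is narrow. The protocol names a weaker, p-value-only method for some thresholds while planning a difference with a CI for another, and the better method is readily available.

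**Conclusion.** The point holds as a reporting improvement for exploratory endpoints. For the 20 shared serotypes (4-fold OPA, 4-fold IgG, OPA at or above LLOQ) and for the IgG and LLOQ thresholds on the 11 novel serotypes, Protocol 10.7.2 states no between-arm method other than an optional Fisher's exact test. That test gives no difference or CI. Its size is 0.7% to 3.2% at 50 per arm and 3.2% to 4.0% at 250 per arm, for assumed response rates of 60% to 95%.

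The figure of 50 per arm is the planned minimum at 65+. With more subjects the conservatism shrinks, but the absence of a reported difference does not change. The main immunogenicity comparison, on the GMR, is unaffected.

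**What to change.** Replace the Fisher sentence in Protocol 10.7.2, and any SAP counterpart not visible in the public copy, with:

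*For the 20 shared serotypes (≥4-fold rise in OPA, ≥4-fold rise in IgG, OPA ≥ LLOQ) and for the IgG and LLOQ thresholds of the 11 non-PCV20 serotypes, the difference in percentages between each VAX-31 dose and PCV20, and between VAX-31 doses, will be presented with a two-sided 95% Miettinen-Nurminen CI, descriptively.*

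Keep the logistic-model analysis and the 0.1 superiority rule as the governing analysis for the 4-fold OPA rise in the 11 novel serotypes.

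The cost is one sentence and a standard risk-difference option in SAS, with no new data and no design change. The downsides are that the interval is asymptotic (largest computed size 5.2% at 50 per arm) and that it will be wide at 65+.
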